**AMENDMENT INCORPORATES:**

- Editorial, administrative changes  
 Therapy changes (IRB approval)

**AMENDMENT RATIONALE AND SUMMARY:**

Section 4.3 (Erlotinib Treatment Dosage and Administration) required erlotinib be held for 3 days prior to SRS in patients who enroll already receiving this agent. Not all participating sites follow this practice, and data are not clear that one approach is best. Therefore, this requirement has been revised to a recommendation. This change is also reflected in sections 6.1 (Time and Events table, specifically the footnotes), section 6.3.2 (Study Assessments) and section 6.7 (Correlative Studies).

In addition, the UNCCN Study Coordinator has been changed to UNCCN Project Manager throughout the protocol.

Section 6.9 (Assessment of Efficacy): clarified that local ablative therapy refers to SRS or other local ablative therapy such as surgery

***THE ATTACHED VERSION DATED 11/18/2014 INCORPORATES THE ABOVE REVISIONS  
ATTACH TO THE FRONT OF EVERY COPY OF PROTOCOL***

**LCCC 1123: Phase II Study Of Stereotactic Radiosurgery or Other Local Ablation  
Followed by Erlotinib for Patients with EGFR Mutation Who Have Previously  
Progressed on an EGFR Tyrosine Kinase Inhibitor (TKI)**

**AMENDMENT INCORPORATES:**

- Editorial, administrative changes  
 Therapy changes (IRB approval)

**AMENDMENT RATIONALE AND SUMMARY:**

The driver for this amendment was clarification of conflicting guidance on the dose and schedule of Stereotactic Radiosurgery (section 4.2) per organ. Guidance now matches the corresponding dosing table for each organ. Specifically:

- Section 4.2.1d (Brain) specified 3 **and** up to 5 fractions per day; now indicates that treatment to be delivered per institutional preference (i.e. on consecutive days versus several per week; one fraction per day)
- Section 4.2.2 (Chest and Lung) specified in sections 4.2.2b and 4.2.2f that patients could have 3-5 **and** 3-10 treatments/fractions; the reference to 3-5 has been removed
- Section 4.2.3 (abdomen) was incomplete. This has been removed as these lesions are rare
- Section 4.2.4 (liver) section 4.2.4f; clarified that 3 to 5 treatments/fractions will be given on consecutive weekdays or every other day
- Section 4.2.5 (spine/soft tissue): deleted reference to dosing schedule in section 4.2.5b as it conflicted with section 4.2.5f; revised dosing schedule in 4.2.5 to indicate dose to be delivered per institutional preference ((i.e. on consecutive days versus several per week; one fraction per day, 1 to 5 fractions)

In addition, the following minor clarifications were made:

- Removed [name] as Co-Investigator as he is no longer at UNC
- Inclusion criteria Section 3.1.5; clarified that progressive disease is assessed via RECIST1.1
- Section 4.3; clarified that 3 day washout means 3 full days without erlotinib
- Section 6.1 Time and events table: added footnotes to clarify tumor evaluations at progression and follow-up; added note that post SRS visit can occur on last day of SRS; clarified windows allowed around study visits
- Section 6.9 (assessment of efficacy); refined definition of patients evaluable for analysis of efficacy

***THE ATTACHED VERSION DATED 6/19/2014 INCORPORATES THE ABOVE REVISIONS***  
**ATTACH TO THE FRONT OF EVERY COPY OF PROTOCOL**

**PROTOCOL AMENDMENT #3: LCCC 1123  
DATED 08/15/2012**

**AMENDMENT INCORPORATES:**

- Editorial, administrative changes
- Scientific changes (IRB approval)
- Therapy changes (IRB approval)
- Eligibility Changes (IRB approval)

This protocol has been amended to allow multicenter sites participating on this trial to utilize their institutional brand of radiosurgery machine.

**Throughout protocol, and particularly in section 4.2:**

Section 4.2: We have edited the study to define standard of care (SOC) parameters for stereotactic radiosurgery that are not specific to the CyberKnife® brand.

**Rationale:** The SOC radiosurgery incorporated in this multicenter protocol was referred to and specific for CyberKnife®. However, the intent of this protocol is not to dictate which SOC radiosurgery is used, as there are many brands of stereotactic radiosurgery. No core content has been modified. The new parameters will not affect in any way how stereotactic radiosurgery is done for UNC patients—it remains SOC. Similarly, it defines the SOC in such a way that parallel procedures will take part at our partner institutions so that their patients will also be treated per SOC.

Minor typographical errors have been corrected throughout protocol

Added Co-Investigators as follows: [name]; [name]

**ATTACH TO THE FRONT OF EVERY PROTOCOL**

**PROTOCOL AMENDMENT #2: LCCC 1123**

**LCCC 1123:**

**AMENDMENT INCORPORATES:**

- Editorial, administrative changes
- Scientific changes (IRB approval)
- Therapy changes (IRB approval)
- Eligibility Changes (IRB approval)

**Section 1.5: Correlative Studies:** Details on VeriStrat® assay revised to:

- Reflect updated references further confirming the validation of this assay
- Removed table 5 with analysis from NCIC BR.21 registrational trial indicating predictive ability of VeriStrat when data adjusted for EGFR mutation status
- Removed reference to full NMR peaks from the MALDI-TOF as VeriStrat does not use NMR (this reference to NMR was also removed from Exploratory Objectives)

**Section 6.7**

- This section has been revised to accommodate blinding. Since there are 4 time points for which samples will be taken, the analysis team from Biodesix, Inc. requested these blood samples be blinded.

**Section 7.3.3**

- Removed Fax # and mailing address to FDA

**Section 9.4**

- Revised to reflect recent changes in LCCC protocol template

**LCCC 1123 – May 15, 2012**

**ATTACH TO THE FRONT OF EVERY COPY OF THIS PROTOCOL**

**PROTOCOL AMENDMENT #1: LCCC 1123**

**LCCC 1123:**

**AMENDMENT INCORPORATES:**

- Editorial, administrative changes
- Scientific changes (IRB approval)
- Therapy changes (IRB approval)
- Eligibility Changes (IRB approval)
- Other

**Throughout study:** Typos corrected

**Sections 4.3 and 5.1.2 :** Manufacturer of erlotinib (Astellas Pharma) has agreed to provide drug free of charge to patients. Sections 4.3 and 5.1.2 were changed to reflect this.

**Sections 7.3 and 7.4:** These were slightly revised to reflect updated safety reporting language for trials conducted under an IND.

## 1.0 BACKGROUND AND RATIONALE

### 1.1 Study Synopsis

This is a single arm phase II trial of 40 patients evaluating a novel treatment strategy for patients with epidermal growth factor receptor (EGFR)-mutant non small cell lung cancer (NSCLC). Eligible patients will have just progressed on a EGFR-tyrosine kinase inhibitor (TKI). In the current trial, all sites of progressive disease will be treated with local ablation (primarily stereotactic radiosurgery) followed by the EGFR-TKI erlotinib until disease progression. We hypothesize that this treatment strategy will lead to a progression free survival of at least 3 months.

### 1.2 EGFR-mutated NSCLC

75% of NSCLC patients present with metastatic disease, with an expected median overall survival (OS) of 10-12 months. Lung cancer progression is multifactorial. Among the influences are cell surface receptors that control intracellular signal transduction pathways. A subset of NSCLC patients harbors an EGFR mutation that particularly drives their cancer, rendering them susceptible to the effects of small molecular EGFR-TKIs such as gefitinib and erlotinib. Almost all patients with the mutation have adenocarcinoma histology. Presence of this mutation is inversely correlated with history of smoking. It is present in 6% of patients with adenocarcinoma who are current smokers, 15% in former smokers, and 52% of never smokers. Treatment of mutated disease with these EGFR-TKIs results in a median PFS (13 months) that exceeds the median OS for non-mutated patients. Beyond the increased survival, toxicity on EGFR-TKIs is very mild compared to cytotoxic chemotherapy, with an acneiform rash and diarrhea being the most common side effects associated with their use.

### 1.3 Erlotinib

The only FDA approved EGFR-TKI in the United States is erlotinib (Tarceva®). This agent is approved for maintenance treatment of locally advanced or metastatic NSCLC that has not progressed after 4 cycles of platinum-based first-line chemotherapy. It is also approved for treatment of locally advanced or metastatic NSCLC after failure of at least one prior chemotherapy regimen.

Several studies have compared chemotherapy to EGFR-TKIs in a variety of contexts within NSCLC. Most relevant to the population to be studied here, the OPTIMAL study compared carboplatin plus gemcitabine to erlotinib for first line therapy of metastatic EGFR-mutant NSCLC. PFS was 13.1 months after erlotinib therapy, as compared to 4.6 months after carboplatin plus gemcitabine (hazard ratio (HR)=0.16, 95% confidence interval (CI) 0.10 to 0.26; p<0.0001).

While these impressive results clearly represent an advance in the treatment of NSCLC, all patients inevitably develop resistance and experience disease

progression within 8-14 months of initiating therapy and thereafter require second line therapy.

The standard therapy for patients with EGFR mutation who progress on erlotinib is cytotoxic chemotherapy. While cytotoxic chemotherapy is active against EGFR mutated NSCLC, it is less active than erlotinib. For example, patients randomized to the chemotherapy arm of OPTIMAL experienced a 4.6 month PFS in their first line of treatment. In addition to being less active, chemotherapy is more toxic than erlotinib, requires intravenous infusion, and ultimately also lasts only a finite duration.

#### **1.4 Rationale for Incorporation of Local Ablative Therapy**

Progression of cancer while on erlotinib may reflect the emergence of a mutant clone. Whether through positive-selection of a resistant clone that was present before starting therapy or from the evolution of such a clone during therapy, it is clear that some of the cancer cells will remain sensitive to erlotinib while others are resistant. This molecular heterogeneity explains the frequently clinically observed mixed response at the time of progression in patients with EGFR mutation on erlotinib. In this situation, many sites of disease remain well controlled with erlotinib while one or a small number of sites progress. If such sites could be eliminated, systemic sensitivity to erlotinib could theoretically be restored. Erlotinib could then be used for systemic control of remaining sites of disease.

Any modality of local control, such as surgery, radiation, or radiofrequency ablation could theoretically be used to eliminate resistant clones. The following section explains the rationale for preferential use of radiation. However, the anatomy of certain sites will be particularly amenable to alternative modalities of local control and the study will allow this.

##### **1.4.1 Radiation for patients with EGFR mutation**

EGFR mutant cells are 500-1,000 fold more sensitive to radiation than wild-type cells, a phenomenon that extends to T790M mutant cells (see Figure 1). In EGFR wild-type cells exposed to radiation, EGFR rapidly translocates to the nucleus where it binds DNA-PK, a key component of non-homologous end-joining repair. In L858R or  $\Delta$ E746-E750 cells, this mechanism of radioresistance is defective. EGFR mutant cells do not halt DNA synthesis or progression to mitosis in response to radiation.

[figure not shown]

Figure 1

These in-vitro findings are supported by human clinical data. Investigators at the Dana Farber Cancer Institute reviewed their outcomes after thoracic radiation between EGFR mutant and wild-type tumors in a retrospective cohort of patients with locally advanced NSCLC. The two-year locoregional relapse rate was 45.5% in EGFR wild-type patients and 19.1% in patients with EGFR mutation. These findings suggest that radiation may be a particularly effective modality for the treatment of EGFR mutant cancers (see Figure 2).

[figure not shown]

Figure 2 (Grey curve EGFR mutant, Black curve EGFR Wild-Type)

#### 1.4.2 Stereotactic Radiosurgery (SRS)

A number of studies have investigated stereotactic radiosurgery (SRS) for the treatment of cancer. SRS is a method for delivering focused high dose

radiotherapy to a tumor while attempting to spare surrounding normal tissues. It is extremely effective at treating small lesions and with appropriate patient selection, has low toxicity. It can be administered via several different modalities, including linear accelerator based (e.g. Varian's Novalis, Accuray's CyberKnife) which can treat both central nervous system and extracranial disease, as well as the GammaKnife which treats intracranial disease exclusively. Much of the focus of research of SRS in lung cancer has been on cure of small lesions in patients who are not candidates for surgery. However, multiple studies have investigated its use in metastatic disease.

Investigators at the University of Rochester Medical Center treated 49 patients with a total of 125 metastatic lesions and achieved a crude local control rate of 94%. Of note, 8 of these patients had lung cancer; there was a tail to the survival curves for both breast cancer and lung cancer (see Figure 3).

[figure not shown]

Figure 3

Another study evaluated only patients with metastatic NSCLC, with only 1 or 2 sites of oligometastatic disease. The long term survival rate of 22% in this study was comparable to older studies utilizing primary surgical resection plus metastectomy of isolated adrenal or brain metastases from NSCLC (see Figure 4).

[figure not shown]

Figure 4

A larger series treated 121 patients with  $\leq 5$  detectable metastases. As shown in the Figure 5 below, 2 year overall and progression-free survival was 50% and 26% and at four years they were 28% and 20%.

[figure not shown]

[figure not shown]
Figure 5

Sufficient data exists on the appropriate use of SRS in body-specific sites that the American Association of Physicists in Medicine (AAPM) has issued guidelines for its use.

### 1.5 Correlative Studies

[figure not shown]
VeriStrat® is a commercially available serum proteomic test that identifies second and third line NSCLC patients who are likely to have a good or poor outcome (as measured by OS) following erlotinib therapy. Serum is analyzed

using Matrix Assisted Laser-Desorption Ionization Time of flight Mass Spectrometry (MALDI-TOF). Eight peaks are analyzed to create a result of “good” or “poor.”

VeriStrat® was initially developed on a training set of 139 patients who were treated with gefitinib and validated on two additional cohorts of patients receiving EGFR TKIs. While the test was able to predict outcomes in patients treated with an EGFR-TKI, it did not distinguish results from patients treated with chemotherapy.

The plot below shows the overall survival by VeriStrat group of one of the original VeriStrat validation cohorts, patients treated in second-line with gefitinib. These data (on file at Biodesix), updated from those published originally, yield a hazard ratio between VeriStrat groups of 0.45 (95% confidence interval: 0.25-0.80), log-rank p=0.006.

[figure not shown]

Interestingly, sera were available from 29 patients who progressed on gefitinib in this series. 22 of these patients were VeriStrat® good at the initiation of the study and 11 (50%) of these converted to VeriStrat® poor at the time of withdrawal from study therapy.

Similar results were found in an analysis of ECOG 3503, a single-arm phase II study of erlotinib for first line therapy of NSCLC. Of 137 enrolled patients, analyzable samples were available on 102. VeriStrat® identified 73% of these as

having a good signature and 27% as having a poor signature. As shown below, both OS and PFS were different for patients with good and poor signatures.

A retrospective analysis of the 441 available pretreatment plasma samples from the NCIC BR.21 registrational study of erlotinib versus placebo in second- and third-line advanced NSCLC patients confirmed that patients classified as VeriStrat Good have significantly better outcomes than those classified as VeriStrat Poor. Multivariate analysis showed that VeriStrat remains a significant predictor of OS when adjusted for other patient characteristics, including EGFR mutation status. In addition to showing in the placebo arm that VeriStrat has a clear prognostic component, this study demonstrated that VeriStrat was predictive of response to erlotinib, with all but one of the 19 responders being classified as VeriStrat Good.

A study has been undertaken to investigate changes in patient VeriStrat classification during the course of gefitinib therapy. It was found that, although VeriStrat classifications remained generally stable during the course of treatment, in approximately 30% of the patients classified as VeriStrat Good at baseline, the classification changed to VeriStrat Poor near progression. Progression in these patients was found to be associated with the development of new lesions. Changes of VeriStrat classification from VeriStrat Poor to VeriStrat Good during the course of treatment were observed, but were rare.

There are several advantages to the use of this assay for biocorrelative studies. First, the test is non-invasive so there would be minimal risk or discomfort to the

patient and no harm to study accrual secondary to reluctance to undergo a biopsy. Second, the test is commercially available and standardized.

Serum will be collected for testing with the VeriStrat® MALDI-TOF assay. Several exploratory objectives will be evaluated. We will evaluate if VeriStrat® at the time of initial progression on TKI predicts for longer PFS or OS. We will evaluate if VeriStrat® following completion of SRS predicts for longer PFS or OS with re-initiation of erlotinib. We will evaluate whether “poor” VeriStrat® signatures ever turn to “good” signatures following SRS. We will evaluate PFS and OS of patients whose signature changes from “poor” to “good.” . We will explore response rates and PFS on subsequent treatments (see section 6.5).

## **2.0 STUDY OBJECTIVES**

### **2.1 Primary Objective**

To estimate PFS after locally ablative therapy and erlotinib in EGFR-mutant NSCLC patients who progressed on prior EGFR-TKI therapy

### **2.2 Secondary Objectives**

**2.2.1** To evaluate local control of sites previously progressive on erlotinib following SRS followed by erlotinib

**2.2.2** To estimate OS after locally ablative therapy and erlotinib in EGFR-mutant NSCLC patients who progressed on prior EGFR-TKI therapy

**2.2.3** To characterize the toxicity of SRS

**2.2.4** To characterize the toxicity of erlotinib when preceded by SRS

### **2.3 Exploratory Objectives**

**2.3.1** To explore if VeriStrat® results at the time of initial progression on EGFR-TKI are associated with longer PFS or OS with the study therapy of SRS followed by erlotinib

**2.3.2** To explore if VeriStrat® results following completion of SRS are associated with longer PFS or OS after re-initiation of erlotinib

**2.3.3** To explore whether “poor” VeriStrat® signatures ever turn to “good” signatures with the study therapy, and to explore PFS and OS of patients whose signature changes

## 2.4 Endpoints

### 2.4.1 Primary

PFS will be measured from the time of initiation of SRS until disease progression or death from any cause

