### 2.4.2 Secondary

- OS will be measured from the time of initiation of SRS until death from any cause
- Local control rate of sites ablated by SRS will be measured both overall and by lesion
- Toxicity of SRS will be measured by NCI CTCAE version 4 following completion of SRS, but prior to erlotinib re-initiation.
- Toxicity of erlotinib will be graded using NCI CTCAE version 4.

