### **3.2 Exclusion Criteria**

Subjects meeting any of the exclusion criteria listed below at baseline will be excluded from study participation:

- 3.2.1** Any unresolved chronic toxicities > grade 2, measured by CTCAE v4.
- 3.2.2** Treatment with any FDA approved or experimental cancer treatment following progression on EGFR-TKI (e.g., radiation or chemotherapy; supportive regimens such as denosumab or zoledronic acid will not result in exclusion)
- 3.2.3** Any history of previous  $\geq$  grade 3 toxicity attributable to erlotinib (except dermatological toxicity)
- 3.2.4** Pregnant or lactating female
- 3.2.5** Any previous radiation to sites of planned SRS. A patient may be deemed eligible in this case if a non-radiation mode of local ablation such as surgical resection is deemed safe and feasible by the PI.
- 3.2.6** History of another malignancy; **exception:** Subjects who have been disease-free for 3 years, or subjects with a history of completely resected non-melanoma skin cancer or successfully treated *in situ* carcinoma are eligible.
- 3.2.7** Concomitant anticancer therapy, immunotherapy, or radiation therapy (no radiation within prior 4 weeks)
- 3.2.8** Evidence of severe or uncontrolled systemic diseases (e.g., unstable or uncompensated respiratory, hepatic, renal, or cardiac disease)
- 3.2.9** Known hypersensitivity reaction or idiosyncrasy to erlotinib
- 3.2.10** Psychological, familial, sociological, or geographical conditions that do not permit compliance with the protocol
- 3.2.11** Any other concurrent condition that in the investigator's opinion would jeopardize compliance with the protocol

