### 4.2 Stereotactic Radiosurgery

All sites of progressive disease will be treated with SRS, unless an alternative locally ablative option is chosen. A maximum of five sites will be treated. If less than five sites have progressed on erlotinib, additional sites up to a total of 5 sites may be treated, at the discretion of the treating radiation oncologist. Guidelines for SRS will be defined by body site, consistent with standard of care radiation, as reviewed below.

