## **6.9 Assessment of Efficacy**

Patients who complete SRS (or other local ablation), receive at least 14 doses of erlotinib, and have their disease re-evaluated at 8 weeks will be evaluable for assessment of the primary objective (PFS). Patients who drop out of the study prior to this point will not be evaluable for the primary objective unless they have received at least 14 doses of erlotinib, and have either clearly progressed or died.

If a patient comes off study at any point after 8 weeks without having progressed or died, they will be censored at their last known progression-free date.

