### **6.9.1 Progression free survival**

Progression free survival will be the primary endpoint of the study. Progression free survival will be measured from the time of initiation of SRS until the time of progression or death. Lesions that progress on initial TKI therapy will be treated with SRS or other locally ablative maneuver. Because of concern for potential antagonism between erlotinib and radiation as well as safety concerns, erlotinib will be held during SRS. This could potentially allow growth of non-treated, erlotinib-sensitive clones during this period, with later disease control on erlotinib. For this reason, non-treated lesions that progress between the pre-treatment and pre-erlotinib reinitiation evaluations will not be counted as progressive disease unless they also progress on the 1st follow-up imaging while on erlotinib. Further, areas treated with SRS are known to sometimes inflame as a consequence of therapy, with no actual disease progression. In clinical practice, radiologist and radiation oncologist assessment of these lesions are predictive of

long-term control. Therefore, clinician judgment will be used for both protocol and treatment decisions in evaluating whether a lesion treated with SRS that appears larger is actually progressive. In all cases, the same judgment must be used for both evaluation of control on study, and clinical decision making.

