#### **6.9.3 Overall survival**

Overall survival will be measured from the time of initiation of SRS until the time of death.

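### PFS and OS are timed from the start of SRS, so evaluable patients ablated by another method have no time zero, and those ablated another way before SRS have a late one

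*Combined protocol and SAP*

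**What the plan says.** **The clock.** Both definitions of PFS begin at the start of SRS: "PFS will be measured from the time of initiation of SRS until disease progression or death from any cause" (Section 2.4.1) and "Progression free survival will be measured from the time of initiation of SRS until the time of progression or death" (Section 6.9.1). Both definitions of OS do the same: "OS will be measured from the time of initiation of SRS until death from any cause" (Section 2.4.2) and "Overall survival will be measured from the time of initiation of SRS until the time of death" (Section 6.9.3). No alternative start date is given, and the analysis plan in Section 8.3 adds none.

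**The population.** The primary and OS objectives (Sections 2.1 and 2.2.2) refer to locally ablative therapy in general. Section 3.1.5 accepts disease suited to SRS or to another local ablation. Section 3.2.5 admits patients whose planned SRS sites were irradiated before, provided that "a non-radiation mode of local ablation such as surgical resection is deemed safe and feasible by the PI". Section 4.2 prescribes SRS for all progressing sites "unless an alternative locally ablative option is chosen". Section 6.9 opens its definition of patients evaluable for PFS with "Patients who complete SRS (or other local ablation), receive at least 14 doses of erlotinib", and the parenthesis there brings in other ablation.

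**The concern.** The start date is narrower than the population. The trial studies local ablation followed by erlotinib, and its primary analysis set includes patients ablated without SRS, but the endpoint can be computed only for patients who have an SRS start date. Neither the Kaplan-Meier estimate of median PFS nor the 3-month progression-free proportion can be formed for a patient without a time zero.

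For a patient who has another on-study ablation first and SRS later, the rule does give a date, but one that falls after study therapy has begun. Whoever builds the analysis file must then supply a start date that the protocol does not contain. In an open-label, single-arm trial that choice should be on paper before outcomes are seen.

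**Working it through.** **1. Can an evaluable patient lack a start date?** Set three rules together.
- Section 4.2 allows another ablation at any progressing site, and Section 3.2.5 admits some patients on that basis.
- Section 6.9 makes a patient who completes SRS or other ablation, takes at least 14 erlotinib doses and is re-evaluated at 8 weeks evaluable for PFS.
- Sections 2.4.1 and 6.9.1 start PFS at SRS and nowhere else.

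A patient whose sites are all treated by surgery meets the first two rules and has no date under the third. Sections 2.4.2 and 6.9.3 leave the same gap for OS.

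**2. Can the start date be late?** Up to five sites may be treated, with a choice of modality (Section 4.2), so mixed treatment is permitted. The order of modalities is not stated. Let d be the time from the first on-study ablation to the start of SRS, and t the time from that ablation to progression or death.
- If t > d, recorded time = t − d, which is shorter than time from the start of study therapy by d.
- If t ≤ d, the event precedes time zero and has no valid recorded time. If SRS is then never given, there is no time zero at all.

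The documents give no value for d. Assuming 2 to 6 weeks, d = 14/30.4375 = 0.46 months to 42/30.4375 = 1.38 months for each affected patient, against a 3-month reference. The two effects run in opposite directions: the first shortens recorded times and the second removes early events.

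**3. Does the protocol contain a suitable anchor?** Yes. Footnote 1 of the Time and Events table counts the pre-study window back from the start of SRS or of local ablative therapy. That footnote governs only baseline assessments.

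**4. Does the fix alter the design?** First reproduce the plan's figure. Section 8.2 gives 80% power for an exact one-sided 0.05 binomial test of 50% against 70% progression free at 3 months with 40 patients.
- P(X ≥ 25 | n = 40, p = 0.5) = 0.077, above 0.05.
- P(X ≥ 26 | n = 40, p = 0.5) = 0.0403, so the rule is at least 26 of 40.
- P(X ≥ 26 | n = 40, p = 0.7) = 0.807.

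The stated 80% reproduces. With time zero defined for every patient, n stays at 40, the rule at 26 and power at 80.7%.

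**The case against.** **SRS is shorthand for the ablation step.** The post-SRS column of the Time and Events table is explained in footnote 2 as following SRS or other local ablation. The entry blood sample is tied to SRS alone in Section 6.7 but to SRS or other ablation in footnote 11. The objectives are written for ablation generally. This stands as evidence of intent, and a statistician would probably substitute the surgery date. It does not supply the definition. Section 6.9.1 uses the narrow term for the clock and, in the very next sentence, the broad one: "Lesions that progress on initial TKI therapy will be treated with SRS or other locally ablative maneuver". The broad term was available and was not used for time zero.

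**Early PFS events are partly governed elsewhere.** Section 6.9 requires at least 14 erlotinib doses even for early dropouts who progress or die. Section 6.9.1 discounts growth of untreated lesions before erlotinib restarts unless they also progress on the first follow-up imaging. No tumour evaluation is scheduled at the post-SRS visit. This stands and limits how many PFS events could be lost between procedures. It does not help patients without a start date, and Section 6.9 states the evaluability rule for PFS, not OS.

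**Surgery before SRS is inferred.** The brain section (4.2.1c) describes SRS to a resection cavity but does not say that the resection was done on study. This also stands: the late clock is a permitted case, not a planned one.

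**Stronger readings that the documents do not support.**
- A reader might infer that failures and complications of non-SRS ablation enter no endpoint. Recurrence at a resected site can be progression under Sections 6.9.10 and 6.9.11. Toxicity is graded after any ablation (Section 6.3.1), every treated patient is evaluable for it (Section 6.8), and adverse events are recorded from day 1 of study treatment (Sections 7.2 and 7.3.1). Limiting the named local control and ablation toxicity endpoints to SRS is a defensible choice of scope.
- A reader might infer that the late clock lowers the 3-month progression-free rate by a calculable amount. That requires events before SRS to count as failures. If only patients event free at SRS are followed, an exponential model leaves the 3-month rate from SRS unchanged.
- A reader might infer a steady loss of power as patients without a date drop out. Nothing in the plan says that they would be dropped, and the exact test is discrete: n = 38 gives 77.4%, but n = 37 (rule at least 24, alpha 0.049) gives 80.7%, the same as n = 40. The test also supplements estimation of median PFS (Section 8.3).

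**Conclusion.** The point holds as a conflict between the stated time zero and the evaluable population. Patients ablated only by a non-SRS method have no start date for PFS or OS. Patients who have another on-study ablation before SRS have a start date after study therapy began.

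The size cannot be computed, because the documents give neither the number of such patients nor the gap between procedures. Section 1.1 describes SRS as the primary form of ablation, so the effect on the results is probably small. The late-start case rests on the assumption that some patients have another on-study ablation before SRS. The case with no start date needs only a patient treated wholly without SRS, which the protocol allows. The confidence interval table and power statement in Section 8.2 are unaffected.

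**What to change.** In Sections 2.4.1, 2.4.2, 6.9.1 and 6.9.3, define time zero for PFS and OS as the first day of any protocol local ablation, whether SRS, surgery or another method. Where a patient has more than one, the earliest on-study procedure sets the date. This agrees with the anchor already used in footnote 1 of the Time and Events table.

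The cost is protocol wording only. Procedure dates are in the source records, and no patients, visits or assessments are added.

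Optionally, report local control and toxicity for non-SRS sites separately by modality. Local control at such sites would need its own definition, since Section 6.9.2 is written around inflammation after SRS. The main fix does not depend on this.
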